### **1.3. Timing of Study analyses**

We will wait to complete this analysis until all study births have taken place and have completed administrative records which have been sent to the study team and matched to

existing analytic files. We will first publish our analysis of the primary outcome (described above) together with secondary outcomes related to maternal and infant health that can shed light on understanding impact estimates for the primary outcome. Following the publication of those results, we plan to produce separate analyses exploring the impact of NFP on maternal and infant outcomes related to the period of childbirth and the postpartum period, antenatal care and mental health care utilization. At 24 months, we plan to examine women's substance abuse, experience of violence, and use of social services, as described above. We may also examine mechanisms of these outcomes, for example, via nurse referrals. If Medicaid coverage is not differential between treatment and control group mothers at 24 months postpartum and the groups remain comparable, we may also explore outpatient mental health treatment patterns for up to two years after birth since the trajectory of depression symptoms in the postpartum period is increasingly understood to vary widely.

#### **1.4. Attrition and Missing Outcome Data**

For the purposes of tracking our sample, we will separately describe the share of mother-baby dyads who fall in three distinct categories where we may observe an index pregnancy, but no index birth or fetal death as follows:

1. *Probable loss of pregnancy*, which is defined as the absence of a matched birth certificate for the index birth and either (a) a matched birth certificate for a subsequent pregnancy where the birth record indicates the mother has had 0 previous live births or (b) the presence of a matched Medicaid claim or hospital discharge record containing a diagnosis or procedure code indicating a probable pregnancy loss during the index pregnancy. Below are the validated ICD-10 diagnosis codes that we use to identify probable pregnancy losses (Table 1.7).

Table 1.7. Probable pregnancy loss diagnosis codes

ICD-10-CM Code	Code Description
O02.0-O03.9	Spontaneous abortion
O00	Ectopic pregnancy
O01	Molar pregnancy

2. *Mother-baby linking error* is defined as the absence of a matched birth certificate for the index birth despite a matched record for the index birth in either Medicaid claims or hospital discharge records. The matched record in Medicaid claims or hospital discharge data must have an admission date within 120 days of the estimated due date reported on the baseline survey and an ICD-10 diagnosis code indicating a live birth according to ICD-9 claims identified by Kuklina et al. (2008) and widely used in claims-based research on birth outcomes.

3. *Unmatched pregnancy outcome* which is defined as the absence of an administrative record for a birth or pregnancy loss episode for the index pregnancy in vital records, Medicaid claims, and hospital discharge data. Some of these "unmatched" cases may eventually become probable pregnancy loss if mothers later match to a birth certificate reporting a first-time birth.

We will report rates of missingness of outcome data for each category listed across the full sample and by treatment arm in order to characterize sample attrition and identify differential attrition across treatment arms in each of these categories.

### **1.5. Endogeneity of Data Sources and Sensitivity Analysis**

Our primary analytic sample for the adverse birth outcome will focus on mothers with fetal deaths or index births observed in vital records, because these records contain more complete data on birth outcomes. In cases where a vital record exists, we will calculate the adverse birth outcome in the manner described in section 1.1. However, a small percentage of mothers who experience a fetal death or live index birth may have an error linking the mother's records to their child's vital records. To accommodate this possibility, we will perform a robustness check that utilizes the sample of mothers with a fetal death or index birth observed in either vital records, Medicaid claims or hospital discharge records.

#### **1.5.1 Calculating Adverse Birth Outcomes Without Vital Records Data**

In this section, we define the calculation of the adverse birth outcome in instances where there is a matched record for the index birth or fetal death in hospital discharge record or Medicaid claims, but not in vital records.

We identify births in hospital discharge records and Medicaid claims using the ICD-10 diagnosis code definition of live birth in Kuklina et al. (2008) and listed in Table 1.8. We will use the ICD-10 diagnosis code Z3A to calculate gestational age. In cases where an ICD-10 code for gestational age is absent from the hospital or Medicaid claim record, we will calculate gestational age at birth using the admission date on the record and the expected due date as given in the baseline survey. The preterm birth component of the adverse birth outcome will be coded as 1 if the gestational age on the health record is less than 37 weeks, or, if the record contains a diagnosis code P07.30-P07.39. The low-birth weight component will be coded as 1 if the record contains a diagnosis code P07.0-P07.18. The SGA component will be coded as 1 if the record contains a diagnosis code of P051. Fetal deaths will be identified with the codes in Table 1.9 when accompanied by an ICD-10 diagnosis code Z3A for gestational age of at least 20 weeks.

---

Table 1.8. Codes to Identify Live Births

ICD-10 Code(s)	Code Description	Exclusion Code
080, 082	Encounter for delivery	No
Z37	Outcome of delivery	No
10D00Z0, 10D00Z1, 10D00Z2	Extraction of products of conception	No
10D07Z3, 10D07Z4, 10D07Z5, 10D07Z6, 10D07Z7, 10D07Z8	Forceps/Vacuum/Breach	No
OW8NXZZ	Episiotomy	No
10A07ZZ, 10A00ZZ, 10A03ZZ, 10A04ZZ, 10A07ZX, 10A07ZW, 10A07Z6, 10A08ZZ	Abortion of products of conception	Yes
0019	Hydatidiform mole, unspecified	Yes
0048	Shock following (induced) termination of pregnancy	Yes
002	Missed abortion	Yes
000	Tubal pregnancy without intrauterine pregnancy	Yes
003	complete or unspecified spontaneous abortion without complication	Yes
008	Complications following ectopic and molar pregnancy	Yes

Table 1.9. Fetal Death Codes

ICD-10 Code(s)	Code Description	Exclusion Code
Z37.1	Single stillbirth	No
Z37.4	Twins, both stillborn	No
Z37.7	Other multiple births, all stillborn	No
P95	Stillbirth on child claims (occasionally appears on Mother claims)	No
036.4	Maternal care for intrauterine death	No

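### SAP 1.5.1: three stillbirth codes also qualify as live births and the fetal-death rule has no fallback when Z3A is missing, so a term stillbirth seen only in claims can trigger no adverse component

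*SAP*

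**What the plan says.** Section 1.5 of SAP Addendum 1 keeps the primary analysis on vital records. It adds a robustness check that brings in mothers whose index birth or fetal death appears only in Medicaid claims or hospital discharge data. Section 1.5.1 gives the scoring rules for those mothers:

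- **Live birth.** Table 1.8 lists the qualifying codes. One row is the undivided category Z37, described as "Outcome of delivery" and marked as not an exclusion code. The exclusion rows cover abortion, mole, ectopic pregnancy and related complications. None covers stillbirth.
- **Fetal death.** "Fetal deaths will be identified with the codes in Table 1.9 when accompanied by an ICD-10 diagnosis code Z3A" for at least 20 weeks. Table 1.9 lists Z37.1 ("Single stillbirth"), Z37.4, Z37.7, P95 and O36.4.
- **Gestational age.** It is taken from Z3A. If Z3A is absent, "we will calculate gestational age at birth using the admission date on the record and the expected due date" from the baseline survey.
- **Preterm.** This component "will be coded as 1 if the gestational age on the health record is less than 37 weeks", or if a P07.30-P07.39 code is present.
- **Low birth weight and SGA.** "The low-birth weight component will be coded as 1 if the record contains a diagnosis code P07.0-P07.18"; SGA works the same way with P051.

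Section 1.2.1 also counts death in the first 7 days as part of the composite. Section 1.5.1 gives no claims rule for it.

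**The concern.** Z37.1, Z37.4 and Z37.7 satisfy both tables, and nothing says which table wins. The overlap alone would do little harm, because the fetal-death component can still be coded 1 on a record that also counts as a live birth. The harm comes from the second gap. The fetal-death rule depends on Z3A, while the date-based fallback is offered only for gestational age in general. A record that fails the fetal-death rule for want of Z3A therefore stays in the sample as a live birth. If it is at term by dates, nothing else in the rules picks it up.

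The robustness check exists to show that the primary result survives failed linkage to vital records. Its outcome should not lose the most serious event in the composite for exactly those mothers. The same code list also decides where these mothers fall in the attrition categories of section 1.4, which are reported by arm.

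**Working it through.** There is no planned figure to reproduce, since the point is one of coding logic. I applied Tables 1.8 and 1.9 and the component rules as written, reading the digit 0 as the letter O in codes such as 080 and 036.4. Each of the five Table 1.9 codes was scored alone, with no P07 or P05 code, in six situations: Z3A of 24 or 38 weeks, and Z3A absent with 24, 36, 37 or 39 weeks by dates. That gives 5 × 6 = 30 records.

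| Code on record | Gestation information | Live birth (Table 1.8) | Fetal-death rule | Preterm | Result |
|---|---|---|---|---|---|
| Z37.1, Z37.4 or Z37.7 | Z3A 24 | yes | met | yes | 1 |
| Z37.1, Z37.4 or Z37.7 | Z3A 38 | yes | met | no | 1 |
| Z37.1, Z37.4 or Z37.7 | no Z3A, 24 or 36 by dates | yes | not met | yes | 1 |
| Z37.1, Z37.4 or Z37.7 | no Z3A, 37 or 39 by dates | yes | not met | no | no component coded 1 |
| P95 or O36.4 | Z3A 24 or 38 | no | met | yes at 24 only | 1 |
| P95 or O36.4 | no Z3A, any of the four | no | not met | n/a | meets neither definition |

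Counts:

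- Score 1: 3 × 4 + 2 × 2 = 16 records.
- Live birth with no component: 3 × 2 = 6 records. Their composite is 0 if a component not coded 1 is read as 0. Otherwise it is undefined.
- Neither definition, so outside the sample: 2 × 4 = 8 records.

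**Effect of the remedies.** Removing the three codes from Table 1.8 is not enough by itself. The 3 × 4 = 12 records with those codes and no Z3A would then meet neither definition. Any that also carried another delivery code would still count as live births and trigger nothing at 37 weeks or more. If the removal is combined with the date fallback in the fetal-death rule, all 30 records score 1.

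**Scale.** Section 1.5 calls the unlinked group small and gives no number. For scale only, Addendum 4, Table 3 shows 3295 + 1637 = 4932 mothers with an index birth. The ranges below are assumptions: 1-5% claims-only, 0.5-2% stillbirths among them, 20-50% of those at term, and 5-50% of those without Z3A.

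- Claims-only stillbirths: 4932 × 0.01 × 0.005 = 0.25 to 4932 × 0.05 × 0.02 = 4.9.
- Mis-scored: 0.25 × 0.20 × 0.05 = 0.002 to 4.93 × 0.50 × 0.50 = 1.2.

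**Section 1.4.** A linking error there requires a claims or discharge record with a live-birth code within 120 days of the due date. If that is programmed from Table 1.8, a claims-only Z37.1, Z37.4 or Z37.7 stillbirth enters this category whether or not Z3A is present. If the three codes are simply excluded, such a record has no home. Table 1.7 covers only O00 to O03.9, the linking-error category needs a live-birth code, and the unmatched category needs the absence of any birth or loss record. The one remaining route is a later birth certificate that shows no previous live birth.

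**The case against.** The best defence is that the failing path is narrow. It needs no vital record, no Z3A, 37 weeks or more by dates and no P07 or P05 code, all at once. It is confined to a robustness check whose data the SAP already treats as less complete. That stands, and it limits the point to a minor correction.

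It can also be said that calling a claims-only stillbirth a linking error is not wrong, because section 1.5 speaks of linkage failing for fetal deaths as well as live births. That stands too. The trouble in section 1.4 is that the category is defined by live-birth codes, so fetal deaths enter it only through the overlap and would fall out once the overlap is removed.

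Some stronger readings are tempting, and the documents do not support them:

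- A reader might infer that unobserved components default to zero. The SAP says when a component is 1 and is silent on the rest.
- A reader might take the remark that a code belongs mainly to child claims as covering low birth weight and SGA. It stands on the P95 row alone. The lack of a vital-record link does not show that no newborn claim is available.
- A reader might put a larger figure on the loss. With 2-5% claims-only mothers, half the events missed and a 20-25% event rate, the pooled rate would fall by 0.02 × 0.5 × 0.20 = 0.2 to 0.05 × 0.5 × 0.25 = 0.6 percentage points. None of those inputs is in the documents, and the loss would come mainly from low birth weight and SGA, not stillbirth. Equal misses in both arms would shrink the effect by only 0.02 × 0.5 = 1% to 0.05 × 0.5 = 2.5% of its size.

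**Conclusion.** The point holds as a defect in the written rules. The live-birth and fetal-death lists overlap on three codes without precedence, and the fetal-death rule omits a fallback that stands in the same section. Together they let a claims-only term stillbirth without Z3A, and without a P07 or P05 code, pass as a live birth with no adverse component. For these three codes, a record with Z3A of at least 20 weeks, or under 37 weeks by dates, still scores 1.

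The consequence is small. Under the assumed ranges, about one record or fewer is mis-scored. The number of claims-only stillbirths whose attrition category depends on the code list is at most about five. The primary vital-records analysis is untouched, and nothing here suggests a bias between arms. A related gap is that the SAP does not say whether low birth weight, SGA and 7-day death are 0 or missing when they cannot be observed.

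**What to change.** 1. In section 1.5.1, exclude Z37.1, Z37.4 and Z37.7 from the Table 1.8 live-birth set. Apply the Table 1.9 fetal-death classification first, so that another delivery code on the record does not override it.
2. When Z3A is absent, let the 20-week threshold use the same admission-date and due-date calculation that the section already gives for gestational age.
3. In section 1.4, give claims-only fetal deaths their own line, or widen the linking-error category to name them. Without this, step 1 would leave nearly all of them in none of the three categories.
4. State whether low birth weight, SGA and death in the first 7 days are scored 0 or missing when no newborn or death record is available.

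A version limited to preterm birth or fetal death may be reported beside the composite. It should not replace it, because the check is meant to test the primary outcome.

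The cost is minor code-list edits and one extra reporting line. Addendum 4 describes the trial manuscripts, birth outcomes among them, as published or forthcoming. If the check has already been run, it should be rerun and the number of reclassified records stated.

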### 1.6. Subgroups

Our primary sub-group is described in the study protocol. Briefly, this subgroup comprises women who have an indicator of poor mental health, are under 19 years of age, or have not

completed high school/received a General Education Development (GED) certificate by the time of enrollment.

In addition to the planned subgroup described above, we may also consider other potential subgroups of particular importance for outcomes related to pregnancy, childbirth, and maternal health. In particular, we may examine the program's impact on the outcomes of Black mothers who are disproportionately at risk for adverse pregnancy and birth outcomes compared to white mothers and who receive postpartum mental health care at disproportionately lower rates. We are also interested in focusing on births where the period of pregnancy and birth occurred prior to the start of the COVID19 pandemic (defined here as March 23, 2020). We expect that the pandemic altered NFP program implementation, clinical practices and utilization of care surrounding pregnancy, as well as families' mental health.

### **1.7. Accounting for Multiple Hypothesis Testing**

For our measures of guideline-recommended antenatal care, we will report a summary index of the outcomes alongside the individual outcomes to be more parsimonious in the number of hypotheses we are testing. The summary index of the four guideline-recommended care outcomes will equal the proportion of the services that the enrollee received. For example, the index will be equal to 0.5 if they received two out of the four services, and equal to 1 if they received all four services.

## **Nurse-Family Partnership Evaluation Analysis Plan Addendum 2: Child Health Outcomes**

*Note: This version of Addendum 2 reflects plans for study design as of January 20, 2021.*

The goal of this analysis plan addendum is to enumerate analysis specific to the child health outcomes.

### **2. Methods**

A full treatment of our empirical approach, primary study outcomes, planned subgroup analyses, and statistical power is given in sections 2.4-2.10 of McConnell et al. (2020). The following sections provide additional context and details of planned analyses for child health-related outcomes.

#### **2.1. Defining the Sample for Analysis**

Our sample for analysis of our primary child-health related outcome will be restricted to mother-baby dyads with an identified index birth as defined in section A.1 of the pre-analysis plan. All analysis will take place at the mother level, where randomization occurs. We discuss how outcomes will be operationalized in the case of multiple births below. We will not restrict the sample based on matching to Medicaid data as the outcomes include utilization that will be observable in all-payer hospital discharge data. For outcomes that rely primarily on Medicaid data (i.e. outcomes related to preventive child health utilization), we may restrict the sample to mother-baby dyads where children retain either partial or continuous Medicaid coverage through the child's first or second year of life. We anticipate that the children of most mothers who enroll in the trial will be eligible for Medicaid for their entire first year of life but we anticipate that more children may drop off of Medicaid during their second year of life, whether because of the need to document eligibility or because of changes in eligibility in the second year of life during some periods of the study (see Table 2). We discuss the potential differences in Medicaid enrollment between control and treatment arms and planned sensitivity analyses and alternative specifications in section 2.4.

#### **2.2. Construction of Study Outcomes**

For our primary study outcome, we will assess the likelihood of experiencing injury, abuse, or neglect during early childhood. This outcome will be defined as a composite measure indicating a health care encounter or mortality associated with International Classification of Diseases (ICD) codes indicating either a major child injury or suspicion of abuse or neglect. We will identify major injury as any medical claim or mortality case that includes an ICD code associated with injury excluding superficial injuries, injuries related to medical care, and injuries stemming from allergic reactions. ICD codes indicating suspected abuse or neglect are derived from validated methods described in Schitzer et al. 2011 and Hooft et al. 2013. Data on early

childhood injury outcomes and suspected abuse or neglect will come from South Carolina all-payer hospital discharge records, Medicaid inpatient and outpatient claims and mortality records. Secondary outcomes related to injuries, suspected abuse or neglect and mortality will decompose the primary outcomes into their composite parts. In the case of multiples, we will consider a mother to experience the outcome if any of her children do and we will average the number of events in cases where the outcome is continuous (i.e. the number of injuries).

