The impact estimate is the regression-adjusted difference between the average outcomes of treatment group participants and control group participants. Impact estimates with p-values less than 0.05 (two-tailed test) will be considered statistically significant and provide evidence that there are likely true differences between the groups as a result of NFP.

In addition to these impact estimates, we will also report the percentage of treatment group participants who reported living in a low-income zip code (LIZC) at the time of study enrollment. (LIZC is defined as a zip code in which fifteen percent (15%) or more of households have incomes below the federal poverty guidelines according to 2012 Census Bureau Data.) Before reporting this percentage, we will use Google Map’s Application Programming Interface (API) to confirm that the participant’s self-reported zip code corresponds with their self-reported street address. To do this, we will send a file of unformatted, raw street addresses, cities, and states to Google’s API to return formatted addresses, including zip code. We will then compare these formatted zip codes to the zip codes reported by each study participant. The file we send to Google Map’s API will include a greater number of ‘fake’ (i.e. non-study participant) addresses than actual addresses, to maintain study participants’ confidentiality.

We will also analyze how the main impact estimates vary within our sample. In particular some mothers and their children may be at higher risk for adverse outcomes such as preterm birth or childhood injury. We will define “risk” based on poverty rate in the census tract in which a mother is enrolled. In order to perform this analysis, we will match participants’ self-reported addresses to census tracts in two ways. First, we will send a de-identified file that will only include a randomly generated ID number and the following address information of unformatted, raw street addresses, cities, states, and zip codes to the United States Census Bureau’s Geocoder tool as well as to the geocoding service, Geocodio. We will match addresses to census tracts using both the Census Bureau Geocoder tool as well as Geocodio in order to be able to cross validate the accuracy of the census tract mapping. Mapping to the wrong census tract or failing to map to a census tract will reduce the accuracy of our analysis. The randomly generated ID number will allow for linking census tract

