5.2. Is there a sample size/power calculation?

Yes: If yes; describe the calculation and the scientific rationale, and, if applicable, by site and key characteristics such as participant demographics

NFP plans to serve 4,000 families in South Carolina between January 2016 and January 2020. Our power analysis suggests that with 4,000 families served in the treatment group, we will need a 2:1 T:C ratio (or 2,000 control group families) to achieve 80% or higher chance of detecting statistically significant effects on two out of the three primary outcomes (pre-term birth, birth spacing, and childhood injury), if the true effect size of the outcomes equals the expected effect size provided by NFP. These expected effect sizes are based on analysis of previous NFP trials and baseline knowledge on the current population of South Carolina's Medicaid-eligible first-time mothers and the assumptions summarized below.

As of May, 2015, the expected effective sizes, in percentage difference between the treatment group and the control groups, is -20% for the measure of pre-term birth, -18% for the measure of birth spacing, and -13% for the measure of child injury. In addition, we need 95% or more of women randomized into the treatment group to receive NFP services, and at most 5% of the control group that receives a home visiting program that has as much impact as NFP. Furthermore, our power calculation is based on the assumption that the distribution of the outcomes variables have the following mean (standard deviation) combinations in the absence of NFP intervention: 0.12 (0.32) for the binary measure for pre-term birth, 0.14 (0.34) for the binary measure of birth spacing, and 0.18 (0.30) for the measure of child injury.

With this set of assumptions, we need to enroll at least 6,000 women into the evaluation with a 2:1 treatment to control ratio to achieve near 80% or higher power. With these numbers we will have roughly 70% power to detect a statistically significant effect on the birth-spacing measure if the true effect size is -18%. We will have a nearly 100% chance to detect a statistical significant effect on the child injury measure if the true effect size is -13%. We will not have sufficient statistical power to detect the expected effect (-20%) on the pre-term birth measure; the minimum detectable effect size with 80% power for the pre-term birth measure is -30%.

6. Recruitment Methods

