Nurse Supervisors will be registered nurses (RNs) who manage the Nurse Home Visitors. At each agency, they will play a role in outreach and recruitment, managing referrals, and, in some cases, enrollment of subjects. Supervisors will have a deep knowledge of the agency they work for and the community served. Ten such supervisors already have experience managing NFP at their agency. One new supervisor will be hired for this project. This role requires a minimum BSN and preferred master's preparation in nursing or a related field.

Nurse Home Visitors will also be RNs with a Bachelor of Science Degree in Nursing who have a very strong knowledge of the study sites. The majority of the nurses already on staff have prior experience implementing the NFP program at the study sites, and several of them have been implementing the program since 2008 when NFP began implementation in South Carolina. Seventeen new nurses will also be hired for this project. These individuals will receive training in research, ethics and study protocols and may have past experience conducting research. A majority of the nurses are residents of the communities being served, and have a background in serving those communities prior to coming to NFP.

Nurse Supervisors and Nurse Home Visitors are trained to screen for various abuses (including substance abuse and domestic violence) and to make referrals to local support services. They are also mandated reporters in the state of South Carolina. As mandated reporters, they must report to the appropriate authorities when they have reason to believe, in their professional capacity, that a child has been abused or neglected.

7.5. Briefly describe how the research facilities and equipment at the research site(s) support the protocol's aims, e.g., private rooms available for interviews, etc.

NFP program staff who are conducting study enrollment at the NFP implementing agencies will be provided private rooms to conduct interviews, and secure tablets with encrypted survey forms to collect baseline data and randomize participants.

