### **2.5. Endogeneity of Data Sources and Sensitivity Analysis**

As discussed above, because child preventative health outcomes will be observed exclusively in Medicaid claims data, we will not observe these outcomes among children who are not enrolled in Medicaid. Because NFP may affect maintenance of Medicaid coverage through the child's first two years of life, child enrollment rates in Medicaid may differ between control and treatment groups.

We will conduct several analyses to determine whether rates of enrollment in Medicaid differ between treated and control groups. First, we will compare enrollment through the first year of life and the first two years of life across treatment and control groups. Even if we do not observe differences in Medicaid enrollment rates between the two groups, the type of children retaining coverage may be influenced by participation in NFP. Therefore, we will also test

whether there are differences in the characteristics of participants between control and treatment groups over the two time periods (12 months and 24 months). We will use a joint F-test to compare characteristics measured at baseline across these two groups using the list of baseline covariates specified in section B.1.

When conducting study analyses, we will report outcomes observed over the first year of life, where more children are likely to be enrolled in Medicaid as well as outcomes over the first 24 months of life. As specified in our study protocol in Section 2.12, we will report our primary outcome excluding data that comes from Medicaid to assess the robustness of our results to this potential source of endogeneity. If we observe significant differences in Medicaid enrollment across treatment and control groups in the second year of life, we may focus more on outcomes that can be measured within the first year of life.

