#### **Outcomes**

Our analysis will focus on pre-registered primary outcomes and indices of secondary outcomes derived from 8 manuscripts that are either published or forthcoming reporting on trial results (birth outcomes, prenatal outcomes, family planning outcomes, postpartum outcomes, mental health outcomes, social service outcomes and child outcomes). These indices will be created using the method developed by Kling, Liebman and Katz (2017). More sophisticated indexing techniques, such as the Optimus index developed by Anderson and Magruder (2023) will also be explored. These outcomes are specified in Table 4-10 with indications of whether participating in NFP would be expected to increase or decrease the outcome. For outcomes related to the use of the emergency department, participation in NFP might be expected to either increase the outcome (i.e. by identifying health challenges that need immediate attention) or decrease the outcome (i.e. by offering a trusted source of information that can reduce unnecessary care-seeking). We include an additional index of ED related outcomes in Table 11.

We will also consider exploratory analyses within the treatment group to determine whether characteristics that predict program outcomes overlap with those that predict program

participation. In this analysis the outcomes will be the number of home visits completed and the duration of participation in the program.

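### The primary child outcome counts coded care encounters, so NFP could change what is recorded as well as true injury, in either direction, and the Medicaid-excluded check addresses coverage only

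*SAP*

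**What the plan says.** SAP Addendum 2, 2.2 defines the primary child outcome: "This outcome will be defined as a composite measure indicating a health care encounter or mortality associated with International Classification of Diseases (ICD) codes" for either a major injury or a suspicion of abuse or neglect. The sources are all-payer hospital discharge records, Medicaid inpatient and outpatient claims, and mortality records. Superficial injuries, injuries from medical care and allergic reactions are left out. Injury, suspected abuse or neglect, and mortality are also reported separately as secondary outcomes.

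SAP 2.5 is concerned that NFP may affect whether children stay on Medicaid. Its remedy is: "we will report our primary outcome excluding data that comes from Medicaid to assess the robustness of our results". Protocol 4.7.1 shows that the hospital encounter data obtained to measure child injury include ED, outpatient surgery and imaging records as well as inpatient stays.

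Only the treatment arm is offered NFP (Protocol 4.1), with visits about every two weeks for most of the programme (SAP B.3). Protocol 7.4 says nurses are trained to screen for abuses and refer to support services, and adds: "They are also mandated reporters in the state of South Carolina". On ED use, SAP Addendum 4 (Outcomes) says that "participation in NFP might be expected to either increase the outcome (i.e. by identifying health challenges that need immediate attention"), and that it might instead decrease it by reducing unnecessary care-seeking. Table 11 accordingly gives child ED visits no desired direction. Table 9 gives the primary composite the direction decrease.

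**The concern.** The outcome measures injury multiplied by the chance that an injury or suspicion is seen and coded. A programme that sends nurses into the homes of one arm could change the second factor. Nurses may prompt a visit that would not have happened, or advise a mother well enough that a visit is avoided. The SAP allows both for ED use in general, but no section in hand carries the thought over to this outcome.

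Dropping Medicaid data removes clinic claims along with the coverage problem. ED records remain, and they are where the SAP itself expects care-seeking to move. A primary estimate, whether null, harmful or beneficial, would therefore mix injury with recording, and the planned check could carry the same mixture.

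**Working it through.** **Inputs.** Protocol 5.1: "Impact estimates with p-values less than 0.05 (two-tailed test) will be considered statistically significant". Protocol 5.2: "we need to enroll at least 6,000 women into the evaluation with a 2:1 treatment to control ratio" (4,000 and 2,000); expected effects include "and -13% for the measure of child injury"; mean (SD) without NFP includes "and 0.18 (0.30) for the measure of child injury". Protocol 5.2 also assumes 95% take-up and at most 5% control exposure to an equally effective programme, a dilution of 0.95 - 0.05 = 0.90. Addendum 4 Table 3: 3,295 and 1,637 mothers with index births. The treated-to-control recording ratio k is an assumption; no document gives it.

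**The plan's own figure.** Protocol 5.2 claims nearly 100% power for child injury.
- Difference: 0.18 × 0.13 = 0.0234.
- SE: 0.30 × √(1/4000 + 1/2000) = 0.00822.
- Power: Φ(0.0234/0.00822 - 1.96) = Φ(0.89) = 81%; with 0.90 dilution, 73%.

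The claim is not reproduced. The same method with dilution gives 68% for birth spacing, close to the stated 70%, so the method is not the cause. There is less spare power to absorb a recording shift than the protocol implies.

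**A true 13% fall with recording ratio k.** Observed difference = 0.18 × (0.87k - 1). Chance of a significant benefit = Φ(|difference|/0.00822 - 1.96).

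| k (assumed) | 0.87k | Observed, points | Chance of significant benefit |
|---|---|---|---|
| 0.90 | 0.783 | -3.9 | over 99% |
| 0.95 | 0.827 | -3.1 | 97% |
| 1.00 | 0.870 | -2.3 | 81% |
| 1.05 | 0.914 | -1.6 | 47% |
| 1.10 | 0.957 | -0.8 | 15% |
| 1.149 (= 1/0.87) | 1.000 | 0.0 | none beyond chance |
| 1.20 | 1.044 | +0.8 | apparent harm |

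**No true effect, k = 0.90.** Difference 0.18 × 0.10 = 0.018; Φ(0.018/0.00822 - 1.96) = Φ(0.23) = 59% chance of a spurious significant benefit.

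**Only suspicion codes inflated.** If they are a share s of events and rise by a factor f, full cancellation needs 0.87 × [(1 - s) + s × f] = 1. So f is about 2.5, 1.75 or 1.5 for s = 10%, 20% or 30% (shares assumed).

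**Scale.** A binary outcome with mean 0.18 has SD √(0.18 × 0.82) = 0.384, not 0.30. The measure powered in the protocol is therefore apparently not the SAP's binary composite. Treated as binary at 18%, the chances at k = 1.00, 1.05 and 1.10 are about 63%, 33% and 11%. The point differences do not change.

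**Precision of an inpatient-plus-mortality version.** The event rate is not in the documents; assume 1%, 2% or 5% in controls, a true 13% fall, and 3,295 against 1,637.

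| Control rate (assumed) | True difference, points | SE, points | Power | Chance of wrong sign |
|---|---|---|---|---|
| 1% | -0.13 | 0.29 | 7% | 33% |
| 2% | -0.26 | 0.41 | 10% | 27% |
| 5% | -0.65 | 0.65 | 17% | 16% |

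Here the wrong-sign chance is Φ(-difference/SE) with the difference taken as positive.

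**The case against.** Several points on the other side stand.

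- The SAP already excludes superficial injuries, arguably the most discretionary encounters, and it separates the components. That split would show whether suspicion codes drive the result, and mortality does not depend on care being sought. It does not repair the non-fatal injury component, which still needs an encounter.
- Child ED use is listed in Table 11. It would signal whether care-seeking differs by arm, though it does not correct the primary estimate.
- The k model is an illustration. It inflates every event equally, deaths and admissions included, and no document supports any particular value.
- SAP Addendum 2, section 2 defers to a published protocol paper that is not in hand and may say more. SAP 2.5 cites its section 2.12 only for the Medicaid exclusion.

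A reader might infer that nurses' mandated reporting feeds suspicion codes straight into the outcome. The documents do not say so: the protocol's Vulnerable Populations section sends those reports to social services or law enforcement, neither of which is a source for this outcome. A code would appear only if a medical encounter followed.

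A reader might also infer that the bias must hide a real fall, or that a null result could never be told apart from better detection. Neither follows. Addendum 4 allows ED use to move either way, so benefit could be exaggerated just as well, and the components and ED outcomes give partial evidence on which is happening.

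**Conclusion.** The primary child outcome is exposed to differential recording in either direction, and no section in hand provides a check aimed at it. The Medicaid-excluded version answers a different question and keeps ED records. On the protocol's inputs, a 5% or 10% relative rise in recording would leave -1.6 or -0.8 of the planned -2.3 points, about 15% would leave nothing, and a fall would overstate benefit. These sizes rest on an assumed uniform shift, on a 0.18 mean that may belong to a different measure, and on a route from nurse contact to coded encounter that is reasonable but not stated for this outcome. Bias is possible, not shown. That warrants a supportive analysis and more careful wording of the result, not a new primary outcome.

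**What to change.** In SAP 2.5, add one supportive version of the primary outcome limited to inpatient discharge records and mortality records, using the same codes. Report it as an estimate with its interval beside the primary result, the planned components and the child ED-use outcomes. State that the primary result is a change in recorded injury or suspicion, which may partly reflect detection in either direction.

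Do not make agreement in sign or significance a condition for interpretation. At the assumed event rates above, a genuine 13% fall would show the wrong sign 16% to 33% of the time, so a gate would often discard a real benefit.

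The cost is one further run on data already in the plan. The downside is fewer events and a wide interval, so the version can qualify the primary result but cannot rescue or overturn it. Inpatient suspicion codes also retain some discretion.

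SAP 2.3 allows versioned changes before analysis starts. Addendum 4 (February 2025) lists child outcomes among manuscripts published or forthcoming, so if that analysis has begun, label the run as added later. Because the components will be read alongside it, also reconcile Table 9, which gives major injury the desired direction increase while the composite containing it is to decrease.
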